#### 2.6.2.3.1 Sensitivity Analysis:

Three sensitivity analyses are planned for secondary endpoint

- The time to the first composite event will be analyzed using Cox's proportional hazard model with factors treatment and in-hospital/out-of-hospital randomization. Hazard ratio for treatment and its 95% CIs will be reported.
- The Kaplan-Meier estimates for time to the first composite events will be provided by the treatment group, in tables and graphs.
- The primary analysis of secondary endpoint 3 will be repeated but data that occurs after diagnosis as COVID-19 positive will be censored at the subject level.

#### 2.6.2.4 Analysis of secondary endpoint 4

The proportional change in NT-proBNP from Baseline to Week 8 will be analyzed using an ANCOVA model similar to the primary efficacy analysis.

- The primary analysis of secondary endpoint 4 will be repeated but data that occurs after diagnosis as COVID-19 positive will be censored at the subject level.

#### 2.6.2.5 Analysis of secondary endpoint 5

The proportional change in high-sensitivity Troponin (hs-Troponin) from Baseline to Week 4 will be analyzed using an ANCOVA model similar to that of the primary efficacy analysis. Log transformed hs-Troponin will be used for analysis. The analysis will be repeated for Week 8.

- The primary analysis of secondary endpoint 4 will be repeated but data that occurs after diagnosis as COVID-19 positive will be censored at the subject level.

#### 2.6.2.6 Analysis of secondary endpoint 6

The dosing level will be summarized by treatment group and in-hospital/out-of hospital randomization status.

Incidence of discontinuations (all causes) will be summarized by treatment group and in-hospital/out-of-hospital randomization status.

- The primary analysis of secondary endpoint 6 will be repeated but data that occurs after diagnosis as COVID-19 positive will be censored at the subject level.

### **2.6.2.7 Analysis of secondary endpoint 7**

Incidence of below adverse events of special interest (AESI) during treatment will be considered.

- Incidence of symptomatic hypotension (Collected in AESI CRF)
- Incidence of hyperkalemia (potassium >5.5 mEq/L) (Collected in AESI CRF)
- Incidence of angioedema (Collected in AESI CRF)
- Incidence of worsening renal function, defined as an increase in serum creatinine of  $\geq 0.5\text{mg/dl}$  and worsening of the eGFR by at least 25% [using Central Lab data from same scheduled or unscheduled visits]

Incidence of adverse events of special interest (AESIs) will be analyzed using a logistic regression model with treatment and in-hospital/out-of-hospital randomization as fixed factors. The model will be used to estimate the odds ratio for treatment and its 95% CIs.

- The number (and proportion) of subjects with AESI will be summarized by treatment.
- The primary analysis of secondary endpoint 7 will be repeated but data that occurs after diagnosis as COVID-19 positive will be censored at the subject level.

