8.4.1 Laboratory evaluations

The local hospital and/or clinic laboratory will be used for all laboratory evaluations required to determine eligibility. If eligibility laboratory assessments were not done during the patient's hospitalization, samples should be collected and sent to the local laboratory. A central laboratory will be used for analysis of all collected specimens from baseline through the final visit. Details on the collections, shipment of samples and reporting of results by the central laboratory will be provided to investigators in the laboratory manual. Results from the local hospital laboratory will be recorded in the eCRF.

Clinically notable laboratory findings are defined in [Appendix 1](#).

Local laboratory assessments may be performed on an as-needed basis for unscheduled visits. Laboratory values that exceed the boundaries of a notable laboratory abnormality must be commented on by the investigator on the source document and additional laboratory evaluations should be performed, as judged appropriate by the investigator. If the laboratory abnormality induces clinical signs or symptoms, or requires therapeutic intervention, then the diagnosis or medical condition must be entered on the patient's AE eCRF. If the laboratory abnormality is the primary reason for an unforeseen hospitalization or otherwise fulfills the seriousness category of an AE, then the procedure for rapid notification of SAEs must be followed. Likewise, if the laboratory abnormality leads to discontinuation from the study drug (temporarily or permanently), the patient must be followed until the abnormality resolves or until it is judged to be permanent. This investigation may include continued monitoring by repeat laboratory testing or by performing additional laboratory tests as deemed necessary by the investigator or the Novartis medical monitor.

Table 8-3 Laboratory Assessments

Test Category	Test Name
Hematology	Hemoglobin, hematocrit, red blood cell count, white blood cell count with differential (Basophils, Eosinophils, Lymphocytes, Monocytes, Neutrophils, Bands, Other (absolute value preferred , %s are acceptable), and platelet count will be measured at Visits 1 (local lab), 2, 7, 11, 13, 15, 16, and 17 (central lab). Hemoglobin A1c will be measured at Visits 2 and 17 (central lab).

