- Drug interrupted/withdrawn

6. its outcome (i.e. recovery status or whether it was fatal)

Conditions that were already present at the time of informed consent should be recorded in medical history of the patient.

Adverse events (including lab abnormalities that constitute AEs) should be described using a diagnosis whenever possible, rather than individual underlying signs and symptoms.

Adverse event monitoring should be continued for at least 30 days following the last dose of study treatment.

Once an adverse event is detected, it must be followed until its resolution or until it is judged to be permanent (e.g. continuing at the end of the study), and assessment must be made at each visit (or more frequently, if necessary) of any changes in severity, the suspected relationship to the interventions required to treat it, and the outcome.

Information about adverse drug reactions for the investigational drug can be found in the Investigator's Brochure (IB).

Abnormal laboratory values or test results constitute adverse events only if they fulfill at least one of the following criteria:

- they induce clinical signs or symptoms
- they are considered clinically significant

- they require therapy

Clinically significant abnormal laboratory values or test results must be identified through a review of values outside of normal ranges/clinically notable ranges, significant changes from baseline or the previous visit, or values which are considered to be non-typical in patients with the underlying disease. Alert ranges for laboratory and other test abnormalities are included in [Appendix 1](#).

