### **2.6.1 Secondary endpoints**

Secondary endpoints include the following:

1. The composite hierarchical outcome consisting of a) time to CV death, b) number and times of HF hospitalizations during follow-up, c) number and times of urgent HF visits during follow-up, and d) time-averaged proportional change in NT-proBNP (from Baseline to Weeks 4 and 8)

2. The cumulative number of recurrent composite events overtime, ie, the total number of composite events of HF hospitalizations, urgent HF visits, and CV death.
3. Incidences of a composite endpoint of worsening renal function defined as:
  - renal death
  - reaching end-stage renal disease (ESRD)
  - $\geq 50\%$  decline in estimated glomerular filtration rate (eGFR) relative to baseline
4. Proportional change in NT-proBNP from Baseline to Week 8
5. Proportional change in hs-Troponin (high sensitivity) from Baseline to Weeks 4 and 8
6. Dosing levels and discontinuations
7. Incidence of adverse events of special interest during treatment
  - Incidence of symptomatic hypotension
  - Incidence of hyperkalemia (potassium  $> 5.5$  mEq/L)
  - Incidence of angioedema
  - Incidence of worsening renal function, defined as an increase in serum creatinine of  $\geq 0.5$  mg/dl and worsening of the eGFR by at least 25% (based on central laboratory data).

All these secondary endpoints will be analyzed using FAS and nominal p-values will be reported. There will be no adjustment for multiplicity.

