### **2.7.3 Laboratory data**

All laboratory data will be listed by treatment group, in-hospital/out-of-hospital randomization, subject, and visit/time and if normal ranges are available abnormalities will be flagged.

Shift tables using the low/normal/high/ classification will be used to compare Baseline to the worst post Baseline value. The number and percentage of subjects with laboratory values will be presented by low/normal/high (low and high) classifications to compare Baseline to worst post Baseline value.

In addition, laboratory values and the change from Baseline for each parameter by visit will be summarized by treatment group sacubitril/valsartan. In the event that there are multiple laboratory values within a visit, the worst value will be summarized.

A summary of hyperkalemia labs by visit will also be presented by treatment group. The highest potassium value for the event and any potassium re-test results will be descriptively summarized. Similarly, creatinine labs will also be presented by visit, treatment group. The highest creatinine value for the event and any creatinine re-test results will be descriptively summarized.

Listings of all laboratory values will be provided. Separate listings for hyperkalemia labs, creatinine labs, and pregnancy tests will also be provided. Any notable laboratory abnormalities will also be flagged.

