#### **Chemistry**

Assessments required for eligibility that need to be measured at Visit 1 include creatinine, potassium, and total bilirubin. Blood urea nitrogen (BUN), glucose, creatinine, total bilirubin, AST (SGOT), ALT (SGPT), alkaline phosphatase, sodium, potassium, chloride, calcium, total protein, albumin, uric acid, and lipid profile be measured at Visits 1 (local lab), 2, 3, 5, 7, 9, 11, 13, 15, 16 and 17 (central lab).

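### Hyperkalemia in secondary endpoint 7 is a laboratory threshold counted only from the AESI form, although central potassium is collected and could be used as central creatinine and eGFR are for the renal event

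*SAP*

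**What the plan says.** SAP 2.6.2.7 gives the source for each event of special interest. For hyperkalemia it reads "Incidence of hyperkalemia (potassium >5.5 mEq/L) (Collected in AESI CRF"). For worsening renal function (a creatinine rise with a fall in eGFR) it specifies "using Central Lab data from same scheduled or unscheduled visits", and SAP 2.6.1 agrees: "worsening of the eGFR by at least 25% (based on central laboratory data"). Incidence is then analyzed by a "logistic regression model with treatment and in-hospital/out-of-hospital randomization as fixed factors", giving an odds ratio and 95% confidence interval.

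Protocol 12.5.1 uses the same potassium threshold and names no source. SAP 2.1.1 (Study phase) defines the double-blind interval for hyperkalemia but also names no source.

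Potassium belongs to the routine chemistry panel. SAP 2.7.3.1 (Chemistry) lists "sodium, potassium, chloride, calcium, total protein, albumin, uric acid, and lipid profile be measured at Visits 1 (local lab") and then at Visits 2, 3, 5, 7, 9, 11, 13, 15, 16 and 17 in the central laboratory; Protocol Table 8-3 matches. Protocol 8.4.1 adds: "A central laboratory will be used for analysis of all collected specimens from baseline through the final visit".

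On adverse event recording, Protocol 10.1.1 states: "Abnormal laboratory values or test results constitute adverse events only if they fulfill at least one of the following criteria". The three criteria are clinical signs or symptoms, clinical significance, and need for therapy.

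**The concern.** The definition asks for nothing beyond a potassium value above 5.5 mEq/L: no symptoms, treatment or investigator judgement. The count, however, depends on someone completing a form. If sites apply the general adverse event rule of Protocol 10.1.1, a patient with an asymptomatic, untreated value that the site does not consider significant meets the endpoint and is counted as event-free.

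The SAP takes the other route for the renal event in the same list and gives no reason for the difference. At stake are the reported incidence of a named tolerability endpoint, the precision of its treatment comparison, and whether the table measures what its label says.

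**Working it through.** **Can the threshold be derived from data already held?** Yes. Central potassium is scheduled from Visit 2 to Visit 17, so flagging any post-baseline value above 5.5 mEq/L is the same kind of programming step as the renal event.

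**Does any text ensure that such values reach the form?** None was found.

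- Protocol 10.1.1 makes a laboratory value an adverse event only conditionally.
- Protocol 8.4.1 requires investigators to comment on notable values, but Appendix 1 defines notable potassium as a rise of more than 20% from baseline. That is not the endpoint threshold. Since 5.5 / 1.20 = 4.58, a patient whose baseline is 4.6 or higher can exceed 5.5 without being notable. At 5.2, the highest screening value that Protocol 5.2 allows, the notable limit is 5.2 × 1.20 = 6.24.
- Appendix 2 calls for elevated values to be repeated and confirmed before action, and its heading uses at or above 5.5 whereas the endpoint uses above 5.5. Without form instructions, sites could differ on unconfirmed values or on a value of exactly 5.5.

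**Do other outputs fill the gap?** SAP 2.7.3 says "A summary of hyperkalemia labs by visit will also be presented by treatment group", with the highest value, re-tests, shift tables and listings. These are descriptive. The shift tables use low/normal/high categories, not 5.5, and none of these outputs supplies the per-patient incidence for the odds ratio.

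**How much could it matter?** The documents state no hyperkalemia rate, capture rate or power for this endpoint, so there is no plan figure to reproduce. The inputs below are assumptions, apart from 450 / 2 = 225 per arm (SAP section 3).

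*Precision, same rate p in both arms.* SE(log OR) = √{2 × [1/(225p) + 1/(225(1−p))]}, with laboratory-defined incidence assumed to be 15%.

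| Form capture | Reported p | SE(log OR) | Relative to full capture |
|---|---|---|---|
| 100% | 15% | 0.264 | 1 |
| 70% | 10.5% | 0.308 | 1.16 |
| 50% | 7.5% | 0.358 | 1.36 |

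*Effect estimate, assumed 10% vs 20% (which arm is which does not matter), equal capture s.* The reported rates are a = 0.10s and b = 0.20s. OR = [a/(1−a)] / [b/(1−b)]. Power is from the two-sided 0.05 normal approximation for two proportions, 225 per arm.

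| s | Events | Risk difference | OR | Power |
|---|---|---|---|---|
| 100% | 22.5 vs 45 | −10 points | 0.44 | 85% |
| 80% | 18 vs 36 | −8 points | 0.46 | 74% |
| 60% | 13.5 vs 27 | −6 points | 0.47 | 60% |
| 40% | 9 vs 18 | −4 points | 0.48 | 43% |

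With 15% vs 20% assumed, power falls from 29% at full capture to 13% at 40% capture, and the OR moves from 0.71 to 0.73. The factor s cancels from the ratio a/b and survives only in (1−b)/(1−a), so the odds ratio changes little while incidence, risk difference and precision all fall.

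**The case against.** The strongest reply is that the harm depends on a form nobody reading these documents can see. Pairing the threshold with the form is consistent with a form triggered by any value above 5.5, and the SAP 2.7.3 summary of the highest potassium per event suggests a potassium-specific record. Protocol 10.1.1 says when a laboratory value is an adverse event; it does not say what goes on the AESI form. Appendix 2 also prompts site action on potassium above 5.5 whether or not there are symptoms, which makes a confirmed value less likely to go unrecorded. All of this stands. A reader might infer that under-reporting is established; the documents show only that nothing prevents it.

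A second reply is that treatment is double-blind, so there is no reason to expect capture to differ by arm, and p-values are nominal. This also stands. A reader might infer a biased treatment comparison; with equal capture the illustration does not support that.

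Third, potassium laboratory data are not ignored: SAP 2.7.3 reports them, so a large shortfall on the form might be noticed. But those outputs do not correct the endpoint 7 estimate.

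Fourth, counting every central value would include hemolyzed or unrepeated results, which Appendix 2 wants confirmed before action. This is a fair objection to a bare any-value rule, and the fix has to deal with it.

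**Conclusion.** The point holds as a mismatch between definition and source. Hyperkalemia is defined by potassium above 5.5 mEq/L, its endpoint 7 incidence comes only from the AESI form, and no text guarantees that every qualifying value reaches that form. Events meeting the definition may be missed, to an unknown extent.

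The likely consequence is understated incidence and lost precision, not a materially biased odds ratio. In the illustration, 70% capture gives a standard error about 16% larger and 50% capture about 36% larger. Those sizes rest on an assumed 15% incidence, assumed capture equal in both arms, and 225 patients per arm; none of the rates is in the documents. If the form's instructions already require every value above 5.5, the loss disappears and the SAP need only say so.

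This is a worthwhile, low-cost improvement to a secondary safety endpoint. It does not affect the primary analysis or the sample size.

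**What to change.** In SAP 2.6.2.7, define hyperkalemia for the logistic model as any post-baseline central laboratory potassium above 5.5 mEq/L, at a scheduled or unscheduled visit, within the during-treatment window, combined with AESI form events so that locally measured cases are kept. Each patient counts once. Exclude results flagged as hemolyzed where the laboratory data carry that flag.

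Report two supporting lines by treatment group: the form-only count, and a count limited to values confirmed on re-test. The gap between the main and form-only lines shows how much the form missed. The confirmed line shows how far the result depends on single values.

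The cost is one derived variable and two table rows, from data already planned, with no new procedure and no change to patient management. Reported incidence may rise, possibly noticeably if form capture is low: in the illustration, from 10.5% to 15% (15 / 10.5 = 1.43, or 43% higher) or from 7.5% to 15% (double). Some unconfirmed single values will count in the main line.

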The proportional change in hs-Troponin (high sensitivity) from baseline to Week 4 will be analyzed using an ANCOVA model similar to that of the primary efficacy analysis. Log-transformed hs-Troponin will be used for analysis. The analysis will be repeated for Week 8.

Analysis of secondary endpoint 6

The dosing level will be summarized by treatment group and in-/out-of-hospital randomization status. Incidence of discontinuations (all causes) will be summarized by treatment group and in-/out-of-hospital randomization status.

Analysis of secondary endpoint 7

Incidence of event will be analyzed using logistic regression model with treatment and in/out-of-hospital randomization as fixed factors. The model will be used to estimate the odds ratio for treatment and its 95% confidence interval.

The number (and proportion) of patients with adverse events of special interest will be summarized by treatment, primary system organ class and preferred term. All these secondary endpoints will be analyzed using FAS and nominal p-values will be reported. There will be no adjustment for multiplicity.

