## 2 Statistical methods

### 2.1 Data analysis general information

All statistical analyses outlined in this SAP will be performed by Novartis Medical & Clinical Solutions. SAS® version 9.3 (or higher) will be used for all analyses.

Data from all centers that participate in this Protocol Amendment 4.0 or previous versions of the Protocols will be combined. All data as collected to date at the time of database lock (DBL) will be included in the analysis.

Unless otherwise specified, for continuous data, the mean, standard deviation (SD), median, first and third quartile, interquartile range, and minimum and maximum values will be presented. Minimum and maximum will be displayed to the same number of decimal places as raw values; mean, median, quartiles, and interquartile range will be presented to 1 additional decimal place; and SD to 2 additional decimal places.

For categorical data, frequencies and percentages will be presented. All statistical tests will be conducted against a two-sided alternative hypothesis, employing a significance level of 0.05.

Due to participants being recruited under the original protocol and participants being recruited under the amended protocols, there will be a mix of participants that are observed for different lengths of time. Therefore, exposure adjusted summaries will be presented for relevant outputs. There will be a mix of participants that are observed for different visits and lengths of time because of the recruitment under the Original Protocol Version 00 and under the amended protocols (01 to 04). However, all the analysis planned here will be a pooled analysis unless otherwise stated.

Additionally, summary statistics will be provided by treatment group and Baseline classification of in-hospital/out-of-hospital randomization group. Geometric means will be used to summarize the NT-proBNP [REDACTED].

All data will be provided in listings in addition to summaries described below.

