**2.6.2.3 Analysis of secondary endpoint 3**

Incidence of a composite endpoint of worsening renal function are defined as:

- renal death (from AE data)
- reaching end-stage renal disease (ESRD) (Sustained eGFR <15mL/min/m^2, chronic dialysis, or renal transplant)
- ≥ 50% decline in estimated glomerular filtration rate (eGFR) relative to baseline [using central laboratory measurements (scheduled or unscheduled visits)]

Among the variables above, none of their components will be adjudicated. The Investigator-reported AE and central laboratory data will be used to identify event of interest in this secondary endpoint 3.

ESRD is defined as one of the following:

- Initiation of dialysis (e.g., hemodialysis, peritoneal dialysis, or continuous eno-venous hemodialysis) after randomization (post-baseline). [from the procedure (PR) data]
- A drop in eGFR from baseline (randomization, i.e. Visit 2) to a value  $<15$  mL/min/1.73m^2 on two consecutive central laboratory measurements [scheduled or unscheduled visits] separated by  $\geq 30$  days. This event will be identified programmatically by the programming team.
- Occurrence of kidney transplantation. [from the procedure (PR) data]

The main analysis of the total number of composite events will be performed using a negative binomial regression model with the count data as the dependent variable. Treatment group and in-hospital/out-of-hospital randomization as fixed-effect factors and log (follow-up duration) as the off-set. The model will be used to estimate event rates and their 95% CIs by treatment group.

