#### **Sample size for the primary endpoint**

This sample size of 450 subjects would have 85% power to detect a 23% reduction in the geometric mean of the proportional change from Baseline to an average of Weeks 4 and 8 in NT-proBNP for the sacubitril/valsartan treatment group. This 23% reduction in geometric mean is equivalent to -0.2614 in natural log scale ( $=\ln(0.77)$ ). The power is estimated assuming a two sided significance level of 0.05, a common SD of 0.85 for change in log transformed NT-proBNP and a 15% rate of missingness in NT-proBNP at baseline or at both Week 4 and Week 8.

nQuery Version 8.4.1.0 (2019) software package is used in calculating the power of the test.

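### The only between-arm comparison of AESIs (secondary endpoint 7) is a logistic odds ratio with no follow-up term, although planned follow-up runs from 8 to about 84 weeks, and no sparse-event method is named for angioedema

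*SAP*

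**What the plan says.** Secondary endpoint 7 covers symptomatic hypotension, hyperkalemia, angioedema and laboratory-defined worsening renal function during treatment. SAP 2.6.2.7 gives one model for all four: "Incidence of adverse events of special interest (AESIs) will be analyzed using a logistic regression model with treatment and in-hospital/out-of-hospital randomization as fixed factors". The output is an odds ratio for treatment with its 95% CI. Protocol 12.5.1 has the same method: "Incidence of event will be analyzed using logistic regression model with treatment and in/out-of-hospital randomization as fixed factors". Beyond this, SAP 2.6.2.7 lists only the number and proportion of patients with each AESI by arm, and a repeat that censors data after a positive COVID-19 diagnosis. SAP 2.6.3 describes the secondary analyses as likelihood based, assuming data are missing at random.

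The SAP recognises that observation time varies. Section 2.1 says "there will be a mix of participants that are observed for different lengths of time", and on that ground promises exposure-adjusted summaries. Section 2.7.1.6 delivers them as adverse event rates per 100 subject treatment years, with exposure counted to the first event. SAP 2.1.1 gives original-protocol patients 8 weeks of double-blind treatment and amended-protocol patients about 84 weeks. SAP 1.1 gives a minimum follow-up of 8 weeks.

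Endpoint 3, the other renal endpoint, is handled differently. Its negative binomial model has "log (follow-up duration) as the off-set" (SAP 2.6.2.3), with Cox and Kaplan-Meier sensitivity analyses beside it.

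**The concern.** A patient observed for 8 weeks and one observed for 84 weeks enter the endpoint 7 model as the same yes/no outcome. The odds ratio then belongs to no stated time point. It depends on how enrolment happened to spread follow-up, and it carries over poorly to another trial or to a prescriber's question about risk by a given time. If one arm were also observed for less time, events in that arm would be missed and the odds ratio would shift.

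The second difficulty is angioedema. Patients with a known history of it are excluded (protocol 5.2, criterion 9), so few events are likely. The plan names no exact or penalised method and no minimum event count for fitting the model.

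These are the trial's named tolerability comparisons, so the estimate should be interpretable and should exist. SAP Appendix B, Section 2, also reuses this model for worsening renal function in data pooled with recently hospitalised PARAGON-HF patients. Median follow-up in PARAGON-HF as a whole was 35 months (protocol 1.1). A study term is added there, but still no follow-up term.

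**Working it through.** **The plan's own figure.** The documents give no expected rate or power for any AESI. The only power statement concerns the primary endpoint: "This sample size of 450 subjects would have 85% power to detect a 23% reduction in the geometric mean", an effect "equivalent to -0.2614 in natural log scale", with "a common SD of 0.85 for change in log transformed NT-proBNP", 15% missingness and two-sided 0.05. With 225 × 0.85 ≈ 191 per arm, the standard error is 0.85 × √(2/191) = 0.0870. Then 0.2614/0.0870 = 3.005, and Φ(3.005 − 1.960) = Φ(1.045) = 85.2%. The figure reproduces. It confirms 225 randomised per arm, which is used below, and says nothing about endpoint 7.

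**Follow-up: assumptions.** Constant hazard h = 0.005 per week in the valsartan arm, follow-up uniform on 8 to 84 weeks, true rate ratio 1.30. None of these comes from the documents except the 8- and 84-week limits.

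- Risk by week t is 1 − exp(−ht): 1 − exp(−0.04) = 3.9% at 8 weeks and 1 − exp(−0.42) = 34.3% at 84 weeks, about a ninefold difference.
- Crude incidence is 1 − [exp(−ha) − exp(−hb)]/[h(b − a)], with a = 8 and b = 84. Valsartan: 20.1%, odds 0.251.
- In the other arm, use hazard 1.30h and multiply a and b by s, the relative length of observation.

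| s | Crude incidence | Odds | Odds ratio |
|---|---|---|---|
| 1.0 | 25.1% | 0.335 | 1.33 |
| 0.9 | 23.0% | 0.298 | 1.19 |
| 0.8 | 20.8% | 0.262 | 1.04 |

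With no true effect, the odds ratio is 1.00 at s = 1 whatever the rate. At assumed rates of 10 to 40 per 100 patient-years, it falls to about 0.95 if one arm is observed 5% less, about 0.89 at 10% less, and 0.78 to 0.80 at 20% less. With equal follow-up and a hazard ratio of 1.5, it is 1.51 to 1.60 at rates from 5 to 40 per 100 patient-years.

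**How much dropout that needs.** If leavers depart at a uniformly distributed point in their planned follow-up, each loses half of it on average. A 10% or 20% shortfall therefore needs about 20 or 40 percentage points more dropout in one arm. With a 5-point excess, the odds ratio under a true 1.30 is about 1.29.

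**Angioedema: assumptions.** True risk p is the same in both arms, with 225 per arm. Let q = (1 − p)^225 be the chance that one arm has no events.

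| p | q | Exactly one arm empty, 2q(1 − q) | Both empty, q² |
|---|---|---|---|
| 0.2% | 0.637 | 46.2% | 40.6% |
| 0.5% | 0.324 | 43.8% | 10.5% |
| 1% | 0.104 | 18.7% | 1.1% |

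If the valsartan risk is 0.2% and the sacubitril/valsartan risk is three times that, exactly one arm is empty with probability 57%.

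**What the fit then does.** Take 2 events against 0, with an assumed 70%/30% in-/out-of-hospital split. An ordinary maximum likelihood fit gives a log odds ratio of 8.5, 12.5 and 16.5 at iterations 12, 16 and 20, with standard errors of 49, 359 and 2,653, so it does not converge. The Firth fit gives 5.0 (95% CI 0.41 to 695), and Fisher's exact p is 0.50.

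**The case against.** A reader might infer that the odds ratio is biased toward no harm. The documents do not support that. Allocation is 1:1 and the planned follow-up rules are the same in both arms. With equal observation the null test is sound, and 1.33 against 1.30 lies slightly further from no effect. The 1.19 and 1.04 need an imbalance that nothing in the documents shows, and that would take heavy differential dropout.

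Nor does stopping study drug clearly end observation. Protocol 9.1.1 keeps such patients in the study and asks them to return for assessments. SAP 2.1.1 allows treatment to end before the study does, and SAP 2.7 runs the on-treatment period to the last study visit. Protocol 6.4.1 points the other way, calling for a prompt end of study visit once drug is stopped completely. Those passages need reconciling, but they do not establish a shortfall in one arm.

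A reader might also infer that the SAP ignores exposure. It does not: crude proportions by arm and exposure-adjusted rates are planned. That objection stands in part. The planned outputs are descriptive and include no between-arm contrast. The rates in 2.7.1.6 are by MedDRA term, so they do not cover worsening renal function as defined from central laboratory values.

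On angioedema, the SAP never says maximum likelihood. This is inferred from 2.6.3 and from the absence of any alternative. A failed fit would be visible in the output, and the counts are reported anyway. When both arms are empty, no method yields a useful comparison.

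Finally, a Cox model is not a full cure. If patients leave because of hypotension or renal decline, censoring is informative and the hazard ratio is biased too.

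**Conclusion.** The omission is real and worth correcting, but modest. Endpoint 7's only between-arm contrast takes no account of follow-up, although the SAP acknowledges unequal observation and adjusts for it in endpoint 3. The certain consequence is an odds ratio tied to an arbitrary mix of 8- to 84-week follow-up. Bias is conditional on one arm being observed for less time. The sizes shown illustrate assumed rates and shortfalls and are not predictions.

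For angioedema, an ordinary likelihood fit would give a zero or infinite odds ratio in roughly one case in five to nearly one in two over the assumed risks of 0.2% to 1%. In a further 1% to 41% of cases both arms would be empty and the odds ratio undefined. The omission and the arithmetic are firm; the AESI rates are assumptions, because the documents give none. Endpoint 7 is secondary, with nominal p-values and no multiplicity adjustment, so the trial's primary conclusion is untouched.

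**What to change.** In SAP 2.6.2.7:

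- For each AESI, add a between-arm model that accounts for follow-up: either a Cox model for time to first event from first dose, or a rate model with log follow-up. Adjust it for in-/out-of-hospital status, as endpoint 3 already does, and use the double-blind risk period of SAP 2.1.1. Give rates per 100 patient-years by arm, including for laboratory-defined worsening renal function.
- Keep the protocol's odds ratio and the crude proportions beside it.
- For angioedema, report counts by arm with an exact or Firth-penalised interval in place of the ordinary likelihood odds ratio. A Cox or rate model also breaks down with an empty arm, so it needs the same treatment there. If neither arm has events, report counts only.
- Record the change in SAP section 4.

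The cost is SAP text and standard code. Exposure to first event is already derived for SAP 2.7.1.6, and laboratory values are tied to visits. There are three downsides: one more effect measure to report; an assumption that censoring is non-informative, which should be stated and read against discontinuation by arm; and interval-censored times for worsening renal function, because scheduled central laboratory visits are up to 16 weeks apart under Amendment 4.
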